**Table 9: Dates of Treatment by Site and Treatment Group**

[Implementation Note: The first period will start with the date of first participant enrollment. Each period displayed will be a year in length except the last period, which will end at the date of final participant enrollment.]

Dates of Dosing	SAR440894 0.3 mg/kg (N=X)	SAR440894 1 mg/kg (N=X)	SAR440894 3 mg/kg (N=X)	SAR440894 10 mg/kg (N=X)	SAR440894 20 mg/kg (N=X)	Placebo (N=X)	All Participants (N=X)
[Site 1]							
Total (Entire period of enrollment)							
DDMMYY-DDMMYY	x	x	x	x	x	x	x
...							
[Site 2]							
Total (Entire period of enrollment)							
DDMMYY-DDMMYY							
...							
All Sites							
Total (Entire period of enrollment)							
DDMMYY-DDMMYY							
...							
Note: N = Number of enrolled participants.							

**Table 10: Ineligibility Summary of Screen Failures**

Inclusion/Exclusion Category	Inclusion/Exclusion Criterion	n a	% b
Any Category	Number of participants failing any eligibility criterion or eligible but not enrolled	x	100
Eligible but Not Enrolled	Any reason eligible but not enrolled	x	xx
	[reason eligible but not enrolled 1]	x	xx
	[reason eligible but not enrolled 2]	x	xx
	[reason eligible but not enrolled 3]	x	xx
Inclusion	Any inclusion criterion	x	xx
	[inclusion criterion 1]	x	xx
	[inclusion criterion 2]	x	xx
	[inclusion criterion 3]	x	xx
Exclusion	Any exclusion criterion	x	xx
	[exclusion criterion 1]	x	xx
	[exclusion criterion 2]	x	xx
	[exclusion criterion 3]	x	xx

a More than one criterion may be marked per participant.b Denominator for percentages is the total number of screen failures.

### 14.1.2 Demographic Data by Study Group

**Table 11: Summary of Categorical Demographic and Baseline Characteristics by Site – Safety Population**

Variable	Characteristic	[Site 1] (N=X)		[Site 2] (N=X)		[Site 3] (N=X)		All Participants (N=X)	
		n	%	n	%	n	%	n	%
Sex	Male	x	xx	x	xx	x	xx	x	xx
	Female								
Ethnicity	Not Hispanic or Latino	x	xx	x	xx	x	xx	x	xx
	Hispanic or Latino								
	Not Reported								
	Unknown								
Race	American Indian or Alaska Native	x	xx	x	xx	x	xx	x	xx
	Asian								
	Native Hawaiian or Other Pacific Islander								
	Black or African American								
	White								
	Multi-Racial								
	Unknown								

Note: N = Number of participants in the Safety Population.

**Table 12: Summary of Continuous Demographic and Baseline Characteristics by Site – Safety Population**

Variable	Statistic	[Site 1] (N=X)	[Site 2] (N=X)	[Site 3] (N=X)	All Participants (N=X)
Age (years)	Mean	x.x	x.x	x.x	x.x
	Standard Deviation	x.x	x.x	x.x	x.x
	Median	x.x	x.x	x.x	x.x
	Minimum	x	x	x	x
	Maximum	x	x	x	x
Height (cm)	Mean	x.xx	x.xx	x.xx	x.xx
	Standard Deviation	x.xx	x.xx	x.xx	x.xx
	Median	x.xx	x.xx	x.xx	x.xx
	Minimum	x.x	x.x	x.x	x.x
	Maximum	x.x	x.x	x.x	x.x
Weight (kg)	Mean	x.xx	x.xx	x.xx	x.xx
	Standard Deviation	x.xx	x.xx	x.xx	x.xx
	Median	x.xx	x.xx	x.xx	x.xx
	Minimum	x.x	x.x	x.x	x.x
	Maximum	x.x	x.x	x.x	x.x
BMI (kg/m  )	Mean	x.xx	x.xx	x.xx	x.xx
	Standard Deviation	x.xx	x.xx	x.xx	x.xx
	Median	x.xx	x.xx	x.xx	x.xx
	Minimum	x.x	x.x	x.x	x.x
	Maximum	x.x	x.x	x.x	x.x

Note: N = Number of participants in the Safety Population.

**Table 13: Summary of Categorical Demographic and Baseline Characteristics by Treatment Group – Safety Population**

Variable	Characteristic	SAR440894 0.3 mg/kg (N=X)		SAR440894 1 mg/kg (N=X)		SAR440894 3 mg/kg (N=X)		SAR440894 10 mg/kg (N=X)		SAR440894 20 mg/kg (N=X)		Placebo (N=X)		All Participants (N=X)	
		n	%	n	%	n	%	n	%	n	%	n	%	n	%
Sex	Male	x	xx	x	xx	x	xx	x	xx	x	xx	x	xx	x	xx
	Female														
Ethnicity	Not Hispanic or Latino	x	xx	x	xx	x	xx	x	xx	x	xx	x	xx	x	xx
	Hispanic or Latino														
	Not Reported														
	Unknown														
Race	American Indian or Alaska Native	x	xx	x	xx	x	xx	x	xx	x	xx	x	xx	x	xx
	Asian														
	Native Hawaiian or Other Pacific Islander														
	Black or African American														
	White														
	Multi-Racial														
	Unknown														

Note: N = Number of participants in the Safety Population.

**Table 14: Summary of Continuous Demographic and Baseline Characteristics by Treatment Group – Safety Population**

Variable	Statistic	SAR440894 0.3 mg/kg (N=X)	SAR440894 1 mg/kg (N=X)	SAR440894 3 mg/kg (N=X)	SAR440894 10 mg/kg (N=X)	SAR440894 20 mg/kg (N=X)	Placebo (N=X)	All Participants (N=X)
Age (years)	Mean	x.x	x.x	x.x	x.x	x.x	x.x	x.x
	Standard Deviation	x.x	x.x	x.x	x.x	x.x	x.x	x.x
	Median	x.x	x.x	x.x	x.x	x.x	x.x	x.x
	Minimum	x	x	x	x	x	x	x
	Maximum	x	x	x	x	x	x	x
Height (cm)	Mean	x.xx	x.xx	x.xx	x.xx	x.xx	x.xx	x.xx
	Standard Deviation	x.xx	x.xx	x.xx	x.xx	x.xx	x.xx	x.xx
	Median	x.xx	x.xx	x.xx	x.xx	x.xx	x.xx	x.xx
	Minimum	x.x	x.x	x.x	x.x	x.x	x.x	x.x
	Maximum	x.x	x.x	x.x	x.x	x.x	x.x	x.x
Weight (kg)	Mean	x.xx	x.xx	x.xx	x.xx	x.xx	x.xx	x.xx
	Standard Deviation	x.xx	x.xx	x.xx	x.xx	x.xx	x.xx	x.xx
	Median	x.xx	x.xx	x.xx	x.xx	x.xx	x.xx	x.xx
	Minimum	x.x	x.x	x.x	x.x	x.x	x.x	x.x
	Maximum	x.x	x.x	x.x	x.x	x.x	x.x	x.x
BMI (kg/m  )	Mean	x.xx	x.xx	x.xx	x.xx	x.xx	x.xx	x.xx
	Standard Deviation	x.xx	x.xx	x.xx	x.xx	x.xx	x.xx	x.xx
	Median	x.xx	x.xx	x.xx	x.xx	x.xx	x.xx	x.xx
	Minimum	x.x	x.x	x.x	x.x	x.x	x.x	x.x
	Maximum	x.x	x.x	x.x	x.x	x.x	x.x	x.x

Note: N = Number of participants in the Safety Population.

### 14.1.3 Prior and Concurrent Medical Conditions

**Table 15: Summary of Participants with Pre-Existing and Concurrent Medical Conditions by MedDRA System Organ Class and Treatment Group – Safety Population**

MedDRA System Organ Class	SAR440894 0.3 mg/kg (N=X)		SAR440894 1 mg/kg (N=X)		SAR440894 3 mg/kg (N=X)		SAR440894 10 mg/kg (N=X)		SAR440894 20 mg/kg (N=X)		Placebo (N=X)		All Participants (N=X)	
	n	%	n	%	n	%	n	%	n	%	n	%	n	%
Any SOC	x	xx	x	xx	x	xx	x	xx	x	xx	x	xx	x	xx
[SOC 1]														
[SOC 2]														

Note: N = Number of participants in the Safety Population; n = Number of participants reporting medical history within the specified SOC. A participant is only counted once per SOC.

## 14.2 Pharmacokinetic/Immunogenicity Data

**Table 16: SAR440894 Concentrations in Plasma by Treatment Group – 0 to 72 h Post Dose – PK Population**

Treatment Group	Nominal Time a (h)							
	0	1	4	8	12	24	48	72
SAR440894 0.3 mg/kg (N=X)	x (x)	x (x)	x (x)	x (x)	x (x)	x (x)	x (x)	x (x)
SAR440894 1 mg/kg (N=X)	x (x)	x (x)	x (x)	x (x)	x (x)	x (x)	x (x)	x (x)
SAR440894 3 mg/kg (N=X)	x (x)	x (x)	x (x)	x (x)	x (x)	x (x)	x (x)	x (x)
SAR440894 10 mg/kg (N=X)	x (x)	x (x)	x (x)	x (x)	x (x)	x (x)	x (x)	x (x)
SAR440894 20 mg/kg (N=X)	x (x)	x (x)	x (x)	x (x)	x (x)	x (x)	x (x)	x (x)

Notes: N = Number of participants in the PK Population. Concentrations are reported in units of  $\mu\text{g/mL}$ . Values of GM (CV %) are shown.

a Times are relative to time of dosing.

**Table 17: SAR440894 Concentrations in Plasma by Treatment Group – 7 to 150 Days Post Dose – PK Population**

Treatment Group	Nominal Time a (days)						
	7	14	28	56	84	112	150
SAR440894 0.3 mg/kg (N=X)	x (x)	x (x)	x (x)	x (x)	x (x)	x (x)	x (x)
SAR440894 1 mg/kg (N=X)	x (x)	x (x)	x (x)	x (x)	x (x)	x (x)	x (x)
SAR440894 3 mg/kg (N=X)	x (x)	x (x)	x (x)	x (x)	x (x)	x (x)	x (x)
SAR440894 10 mg/kg (N=X)	x (x)	x (x)	x (x)	x (x)	x (x)	x (x)	x (x)
SAR440894 20 mg/kg (N=X)	x (x)	x (x)	x (x)	x (x)	x (x)	x (x)	x (x)

Notes: N = Number of participants in the PK Population. Concentrations are reported in units of  $\mu\text{g/mL}$ . Values of GM (CV %) are shown.  
a Times are relative to time of dosing.

**Table 18: SAR440894 Concentrations in Plasma, SAR440894 0.3 mg/kg – 0 to 72 h Post Dose – PK Population**

[Implementation Note: Mark concentrations collected out of window with an asterisk (\*) next to the concentration and include the footnote: “Samples collected out of window are noted by as asterisk (\*).”]

Mark concentrations collected substantially out of window with two asterisks (\*\*) next to the concentration and include the footnote: “Samples collected substantially out of window are noted by two asterisks (\*\*).”

Mark imputed concentration times with three asterisks (\*\*\*) next to the concentration and include the footnote: “Samples with imputed collection times are noted by three asterisks (\*\*\*).”]

Participant ID	Nominal Time a (h)							
	0	1	4	8	12	24	48	72
PH2.00123	x	x	x	x	x	x	x	x
PH2.00124	x	x	x	x	x	x	x	x
PH2.00125	x	x	x	x	x	x	x	x
...								
Statistics								
Nb	x	x	x	x	x	x	x	x
Mean	x	x	x	x	x	x	x	x
SD	x	x	x	x	x	x	x	x
GM	x	x	x	x	x	x	x	x
CV%	x	x	x	x	x	x	x	x
Min	x	x	x	x	x	x	x	x
Max	x	x	x	x	x	x	x	x

Notes: Concentrations are reported in units of  $\mu\text{g/mL}$ .  
 [Out of window footnotes here, if applicable]

a Times are relative to time of dosing.

b Number of data points used to compute the summary statistics. For calculated of summary statistics, BQL values were imputed to 0 if the sample was taken before the first measurable PK sample with a concentration above the LLOQ. BQL values were treated as missing otherwise.

**Table 19: SAR440894 Concentrations in Plasma, SAR440894 0.3 mg/kg – 7 to 150 Days Post Dose – PK Population**

[Implementation Note: Mark concentrations collected out of window with an asterisk (\*) next to the concentration and include the footnote: “Samples collected out of window are noted by as asterisk (\*).”]

Mark concentrations collected substantially out of window with two asterisks (\*\*) next to the concentration and include the footnote: “Samples collected substantially out of window are noted by two asterisks (\*\*).”

Mark imputed concentration times with three asterisks (\*\*\*) next to the concentration and include the footnote: “Samples with imputed collection times are noted by three asterisks (\*\*\*).”]

Participant ID	Nominal Time a (days)						
	7	14	28	56	84	112	150
PH2.00123	x	x	x	x	x	x	x
PH2.00124	x	x	x	x	x	x	x
PH2.00125	x	x	x	x	x	x	x
...							
Statistics							
Nb	x	x	x	x	x	x	x
Mean	x	x	x	x	x	x	x
SD	x	x	x	x	x	x	x
GM	x	x	x	x	x	x	x
CV%	x	x	x	x	x	x	x
Min	x	x	x	x	x	x	x
Max	x	x	x	x	x	x	x

Notes: Concentrations are reported in units of  $\mu\text{g/mL}$

[Out of window footnotes here, if applicable]

a Times are relative to time of dosing.

b Number of data points used to compute the summary statistics. For calculated of summary statistics, BQL values were imputed to 0 if the sample was taken before the first measurable PK sample with a concentration above the LLOQ. BQL values were treated as missing otherwise.

**Tables with Similar Format:**

**Table 20:** SAR440894 Concentrations in Plasma, SAR440894 1 mg/kg – 0 to 72 h Post Dose – PK Population

**Table 21:** SAR440894 Concentrations in Plasma, SAR440894 1 mg/kg – 7 to 150 Days Post Dose – PK Population

**Table 22:** SAR440894 Concentrations in Plasma, SAR440894 3 mg/kg – 0 to 72 h Post Dose – PK Population

**Table 23:** SAR440894 Concentrations in Plasma, SAR440894 3 mg/kg – 7 to 150 Days Post Dose – PK Population

**Table 24:** SAR440894 Concentrations in Plasma, SAR440894 10 mg/kg – 0 to 72 h Post Dose – PK Population

**Table 25:** SAR440894 Concentrations in Plasma, SAR440894 10 mg/kg – 7 to 150 Days Post Dose – PK Population

**Table 26:** SAR440894 Concentrations in Plasma, SAR440894 20 mg/kg – 0 to 72 h Post Dose – PK Population

**Table 27:** SAR440894 Concentrations in Plasma, SAR440894 20 mg/kg – 7 to 150 Days Post Dose – PK Population

**Table 28: Summary Statistics for SAR440894 PK Parameters in Plasma by Treatment Group – PK Population**

PK Parameter (Units)	SAR440894 0.3 mg/kg	SAR440894 1 mg/kg	SAR440894 3 mg/kg	SAR440894 10 mg/kg	SAR440894 20 mg/kg
C max , (µg/mL)	x (x)	x (x)	x (x)	x (x)	x (x)
C max /Dose, (µg/mL)/(mg/kg)	x (x)	x (x)	x (x)	x (x)	x (x)
T max , (h)	x (x - x)	x (x - x)	x (x - x)	x (x - x)	x (x - x)
C min , (µg/mL)	x (x)	x (x)	x (x)	x (x)	x (x)
AUC (0-last) , (µg*h/mL)	x (x)	x (x)	x (x)	x (x)	x (x)
AUC (0-last)/Dose , (µg*h/mL)/(mg/kg)	x (x)	x (x)	x (x)	x (x)	x (x)
AUC (0-inf) , (µg*h/mL)	x (x)	x (x)	x (x)	x (x)	x (x)
λ Z , (1/h)	x (x)	x (x)	x (x)	x (x)	x (x)
t 1/2 , (h)	x (x)	x (x)	x (x)	x (x)	x (x)
CL, (L/h/kg)	x (x)	x (x)	x (x)	x (x)	x (x)
V d , (L/kg)	x (x)	x (x)	x (x)	x (x)	x (x)

Note: Values of GM (CV %) are shown, except for Tmax for which values of median (min-max) are shown.

**Table 29: Summary Statistics for SAR440894 PK Parameters in Plasma, SAR440894 0.3 mg/kg – PK Population**

Statistics	C max ( $\mu$ g/mL)	C max /Dose ( $\mu$ g/mL)/(mg/kg)	T max (h)	C min ( $\mu$ g/mL)	AUC (0-last) ( $\mu$ g*h/mL)	AUC (0-last)/Dose ( $\mu$ g*h/mL)/(mg/kg)	AUC (0-inf) ( $\mu$ g*h/mL)	$\lambda z$ (1/h)	t 1/2 (h)	CL (L/h/kg)	V d (L/kg)
N	X	X	X	X	X	X	X	X	X	X	X
Mean	X	X	X	X	X	X	X	X	X	X	X
SD	X	X	X	X	X	X	X	X	X	X	X
GM	X	X	X	X	X	X	X	X	X	X	X
CV%	X	X	X	X	X	X	X	X	X	X	X
Min	X	X	X	X	X	X	X	X	X	X	X
Max	X	X	X	X	X	X	X	X	X	X	X

Note: N = Number of participants used to calculate the summary statistics.

**Tables with Similar Format:****Table 30: Summary Statistics for SAR440894 PK Parameters in Plasma, SAR440894 1 mg/kg – PK Population****Table 31: Summary Statistics for SAR440894 PK Parameters in Plasma, SAR440894 3 mg/kg – PK Population****Table 32: Summary Statistics for SAR440894 PK Parameters in Plasma, SAR440894 10 mg/kg – PK Population****Table 33: Summary Statistics for SAR440894 PK Parameters in Plasma, SAR440894 20 mg/kg – PK Population**

**Table 34: Proportion of Participants with a Positive Screening Assay by Treatment Group and Time Point – Immunogenicity Population**

Time Point	Positive Screening Assay													
	SAR440894 0.3 mg/kg (N = X)		SAR440894 1 mg/kg (N = X)		SAR440894 3 mg/kg (N = X)		SAR440894 10 mg/kg (N = X)		SAR440894 20 mg/kg (N = X)		Placebo (N = X)		All Participants (N = X)	
	n	%	n	%	n	%	n	%	n	%	n	%	n	%
Baseline	x	xx												
Day 56														
Day 112														
Day 180														

Note: N = Number of participants in the Immunogenicity Population.

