### **Participant Replacement:**

Participants who withdraw prior to receiving study product will be replaced. Up to 1 participant per cohort may withdraw after dosing but before Day 112 without being replaced. Should more than 1 participant from the same cohort withdraw from the study before Day 112, they will be replaced. Any decision to replace a participant who withdraws after receiving study product will be documented in a note to file. Replacement participants will receive the same treatment as the participant being replaced.

Participants who withdraw after receiving study product will be encouraged to continue Follow-up (with participant's consent) for safety and will be asked to complete the ET visit if they do not wish to be followed per protocol. If a participant withdraws following dosing, analyses for safety, PK, and immunogenicity will be completed on blood samples already obtained.

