## 6. GENERAL STATISTICAL CONSIDERATIONS

### 6.1. General Principles

Unless otherwise specified, continuous variables will be summarized by the following descriptive statistics: the number of participants with non-missing data included in the analysis (n), mean, standard deviation (SD), median, minimum value (min), and maximum value (max). Summary statistics for discrete data will include frequencies and proportions and may include confidence intervals (CIs) for the proportion. When 95% CIs are given for a proportion, exact (Clopper-Pearson) CIs will be used, unless otherwise specified.

All randomized participants will be included in summaries of participant demographics. The Safety Population will be used for summaries of safety endpoints, the PK Population will be used for summaries of PK endpoints, and the Immunogenicity Population or the Pharmacokinetics – Immunogenicity Subset Population will be used for summaries of immunogenicity endpoints. Denominators for clinical, clinical laboratory, VS, and ECG results at planned study time points will be the number of participants in the Safety Population with available results at the specified time point for that parameter. Denominators for the conceptual “Maximum Severity Post Baseline” time point for clinical, clinical laboratory, VS, and ECG results will be the number of participants with an observed result for the parameter obtained post-dose. Unless otherwise specified, denominators for all other safety endpoints will be the number of participants in the Safety Population. All tables will be annotated with the total population size relevant to that table/group, including any missing observations.

The sort order for listings is indicated in the implementation note for each listing shell. The sort order of treatment groups is given in [Section 3](#). The sort order of clinical laboratory tests, VS, and ECG parameters is described in [Section 9](#).

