### **6.3.3. Immunogenicity Population**

The Immunogenicity Population will include all participants who receive any amount of study product and contribute at least one post-infusion plasma sample for immunogenicity testing for which valid results are reported.

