## 11. IMMUNOGENICITY

Plasma samples for ADA measurements will be collected pre-infusion (60 to 0 minutes prior to start of infusion), Day  $56 \pm 4$ , Day  $112 \pm 7$ , Day  $150 \pm 7$ , and ET. For immunogenicity assays, baseline will be defined as the pre-infusion ADA measurement collected on Day 1. Unless otherwise specified, the immunogenicity population will be used when summarizing ADA results.

Positive and negative results for immunogenicity assays will be defined as described in [Section 4.5.3](#). ADA titers may be determined in the case of positive ADA results. Positive post-dose ADA results for participants with baseline ADA results will be further defined as treatment-induced ADA, treatment-boosted ADA, or pre-existing ADA, with the definitions of these provided in [Section 4.5.3](#).

The proportion of participants with a positive screening assay will be summarized by dose group and time point in [Table 34](#). The proportion of participants with negative, treatment-induced, treatment-boosted, and pre-existing ADA results will be summarized by dose group and post-dose time point in [Table 35](#). The incidence of ADA, defined as either treatment-induced or treatment-boosted ADA at any time point, will be summarized by dose group in [Table 36](#).

Reverse cumulative distribution (RCD) curves will be presented for post-dose ADA titers by dose group and time point in [Figure 11](#).

If positive ADA results are ascertained and ADA titers are determined, summary statistics of ADA titers including mean titer, SD, median titer, min titer, max titer, geometric mean titer (GMT), geometric mean fold rise (GMFR) from baseline, and percent of participants with at least a 4-fold rise in titer from baseline will be presented by dose group and time point in [Table 37](#). GMT, GMFR, and percent of participants with at least a 4-fold rise in titer from baseline will be presented with corresponding 95% confidence intervals. ADA GMTs will also be presented in [Figure 12](#) by dose group and time point.

Individual ADA assay results will be presented in [Listing 12](#).

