## 14.1 Description of Study Subjects

### 14.1.1 Disposition of Subjects

**Table 7: Participant Disposition by Treatment Group**

Participant Disposition	SAR440894 0.3 mg/kg (N=X)		SAR440894 1 mg/kg (N=X)		SAR440894 3 mg/kg (N=X)		SAR440894 10 mg/kg (N=X)		SAR440894 20 mg/kg (N=X)		Placebo (N=X)		All Participants (N=X)	
	n	%	n	%	n	%	n	%	n	%	n	%	n	%
Screened	--	--	--	--	--	--	--	--	--	--	--	--	x	--
Enrolled/Randomized	x	100	x	100	x	100	x	100	x	100	x	100	x	100
Received Treatment	x	xx	x	xx	x	xx	x	xx	x	xx	x	xx	x	xx
Received Full Planned Amount of Treatment a	x	xx	x	xx	x	xx	x	xx	x	xx	x	xx	x	xx
Had at Least One Quantifiable Post-Infusion Plasma Drug Concentration Measured														
Completed All PK Blood Draws														
Had at Least One Post-Infusion Immunogenicity Blood Draw with Valid Results														
Completed all Immunogenicity Blood Draws														
Completed Final Study Visit (Study Day 150) a														
Early Termination a														

Note: N = Number of enrolled participants.

aRefer to Listing 16.2.1 for reasons participants discontinued or terminated early.

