**Table 35: Post-Infusion ADA Assay Results by Planned Time Point and Treatment Group – Immunogenicity Population**

Time Point	Treatment Group	N	ADA Result			
			Treatment-Induced ADA n (%)	Treatment-Boosted ADA n (%)	Pre-existing ADA n (%)	Negative n (%)
Day 56	All Participants	X	x (%)	x (%)	x (%)	x (%)
	SAR440894 0.3 mg/kg	X	x (%)	x (%)	x (%)	x (%)
	SAR440894 1 mg/kg	X	x (%)	x (%)	x (%)	x (%)
	SAR440894 3 mg/kg	X	x (%)	x (%)	x (%)	x (%)
	SAR440894 10 mg/kg	X	x (%)	x (%)	x (%)	x (%)
	SAR440894 20 mg/kg	X	x (%)	x (%)	x (%)	x (%)
	Placebo	X	x (%)	x (%)	x (%)	x (%)
Day 112	All Participants	X	x (%)	x (%)	x (%)	x (%)
	SAR440894 0.3 mg/kg	X	x (%)	x (%)	x (%)	x (%)
	...	X	x (%)	x (%)	x (%)	x (%)
	Placebo	X	x (%)	x (%)	x (%)	x (%)
Day 150	All Participants	X	x (%)	x (%)	x (%)	x (%)
	SAR440894 0.3 mg/kg	X	x (%)	x (%)	x (%)	x (%)
	...	X	x (%)	x (%)	x (%)	x (%)
	Placebo	X	x (%)	x (%)	x (%)	x (%)
Note: N=Number of participants in the Immunogenicity Population in each treatment group with results for the given time point, excluding those for whom treatment-induced, treatment-boosted, and pre-existing ADA cannot be assessed.						

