**Table 36: Incidence of ADA by Treatment Group – Immunogenicity Population**

Treatment Group	N	Incidencea of ADA	
		n	%
All Participants	x	x	xx
SAR440894 0.3 mg/kg			
SAR440894 1 mg/kg			
SAR440894 3 mg/kg			
SAR440894 10 mg/kg			
SAR440894 20 mg/kg			
Placebo			

Notes: N = Number of participants in the Immunogenicity Population, excluding those for whom treatment-induced and treatment-boosted ADA cannot be assessed.

a Incidence of ADA is defined as either treatment-induced or treatment-boosted ADA at any time point

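### The Table 34 shell gives per-visit ADA screening-positive percentages with only the whole Immunogenicity Population as N, and its last row is a Day 180 visit that is not in the schedule.

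*SAP*

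**What the plan says.** SAP section 11 (Immunogenicity) introduces the display: "The proportion of participants with a positive screening assay will be summarized by dose group and time point in" Table 34. It names no denominator.

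The Table 34 shell has one column per treatment group, each headed by a single N, with n and % beneath. The rows are Baseline, Day 56, Day 112 and Day 180. The footnote is "Note: N = Number of participants in the Immunogenicity Population". There is no count of participants tested at each visit.

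Other parts of the SAP bear on this:

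- **Section 6.3.3** admits anyone who received any study product and did "contribute at least one post-infusion plasma sample for immunogenicity testing for which valid results are reported".
- **Section 6.1** sets available-result denominators for clinical, clinical laboratory, vital-sign and ECG results. ADA is not on that list. It also says "All tables will be annotated with the total population size relevant to that table/group, including any missing observations".
- **Table 35**, same population, defines its denominator by visit: "N=Number of participants in the Immunogenicity Population in each treatment group with results for the given time point".
- **Table 37**, same population, keeps N in the header but adds an n of participants with available results at each visit.
- **Sections 4.5.3 and 11**, like protocol section 7.2.2, schedule ADA samples pre-infusion, at Day 56 (±4), Day 112 (±7) and Day 150 (±7), and at early termination (ET).

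**The concern.** A percentage by visit needs a denominator by visit. If the percentage is n over the header N, a population member with no valid result at that visit cannot be in the numerator but stays in the denominator. The reported positivity is then too low whenever samples are missing. The reader cannot correct it from the table, because the number tested is not shown. In groups of six, one missing sample moves the percentage visibly.

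The Day 180 label is a separate fault. Table 34 is the display for the by-visit screening summary that protocol section 10.5.3 calls for, and the immunogenicity endpoint runs to Day 150. A programmer following the shell literally would produce an empty row and no row for the final visit.

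**Working it through.** **Time point.** The plan's figure is Day 180. The last scheduled ADA visit is Day 150 ±7, that is Day 143 to Day 157. Day 180 falls 180 − 157 = 23 days after that window closes. Tables 35 and 37 both end at Day 150. The figure does not reproduce from any schedule in the two documents.

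**Group sizes.** From SAP Table 1: 5 cohorts × (6 active + 2 placebo) = 40. That gives six per dose group and ten in pooled placebo.

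**Who can be in N without a result at a visit.** This follows from the rule in section 6.3.3:

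- A participant who leaves before Day 56 and gives no ET sample is not in the population. There is no effect on the percentage.
- A participant who leaves before Day 56 and gives a valid ET sample is in N but has no result at any scheduled post-dose visit. Table 34 has no ET row.
- A participant with a valid Day 56 sample who later leaves, misses a visit or has an invalid result is in N but lacks the later visit.
- A participant with no valid baseline result but a valid later one is in N and affects the Baseline row.

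**Size.** Let N be the members of the population in a group, m those without a valid result at the visit, and k the positives.

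- Shown, on the plain reading: k/N
- Among those tested: k/(N − m)
- Ratio of shown to tested: (N − m)/N

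The values of k and m below are illustrations. The documents give no expected ADA rate or missing-sample rate.

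| Group | N | m | k | Shown k/N | Tested k/(N − m) | Ratio |
|---|---|---|---|---|---|---|
| Dose group | 6 | 0 | 1 | 16.7% | 16.7% | 1 |
| Dose group | 6 | 1 | 1 | 16.7% | 20.0% | 5/6 = 0.833 |
| Dose group | 6 | 1 | 2 | 33.3% | 40.0% | 0.833 |
| Dose group | 6 | 2 | 1 | 16.7% | 25.0% | 4/6 = 0.667 |
| Pooled placebo | 10 | 1 | 1 | 10.0% | 11.1% | 9/10 = 0.900 |
| All participants | 40 | 5 | 4 | 10.0% | 11.4% | 35/40 = 0.875 |

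The relative understatement in a dose group of six is 1 − 5/6 = 16.7% with one missing and 1 − 4/6 = 33.3% with two missing.

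**Link to the withdrawal rule.** SAP section 4.3.3 says: "Up to 1 participant per cohort may withdraw after dosing but before Day 112 without being replaced". One missing participant is therefore within what the plan tolerates. The allowance is per cohort of eight, so the person may be a placebo recipient, and the effect arises only if that person is in the population at all. Replacement does not necessarily remove it, because a replaced participant's samples are still analysed. Suppose two of six active participants withdraw after valid ET samples and both are replaced. Then N = 8 with six tested at Day 150, and two positives are 2/6 = 33.3% of those tested but 2/8 = 25.0% of N.

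**The case against.** The strongest reply is that the footnote only defines the header N. Section 6.1 requires every table to carry its total population size, missing observations included, so N may be an annotation and not the divisor. Table 37 has the same kind of header N while its statistics rest on available results. Section 6.5 rules out imputation for missing values, which sits badly with scoring untested people as not positive. This stands to the extent that a reader who infers a written rule treating missing samples as negative goes further than the documents do. It does not remove the point. Table 34 offers no other denominator, section 6.1 has no by-visit rule for ADA, and Tables 35 and 37 state by-visit counts where Table 34 does not.

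Three further inferences are tempting but unsupported:

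- **That Table 36 (ADA incidence) has the same fault**, because someone with only an early ET sample would be counted negative. Its note already leaves out some participants: "excluding those for whom treatment-induced and treatment-boosted ADA cannot be assessed". Nothing in the documents says that an early-ET-only participant is assessable. ET is itself a planned ADA collection. Requiring a Day 56 or later sample for negatives while counting positives at any time would make entry to the denominator depend on the outcome and push incidence upward.
- **That the bias is worst at late visits because ADA appears late, or that it differs by dose.** The documents say nothing on when ADA is expected or on dropout by dose.
- **That Tables 34 and 35 should share a denominator.** Table 35 also drops participants whose ADA category cannot be assessed, so the two may properly differ after correction.

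It is also fair to say the stakes are low. A screening positive is not an ADA positive until confirmed (section 4.5.3), ADA status and incidence are reported in Tables 35 and 36, and no hypothesis is tested.

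**Conclusion.** The point holds as a minor one. The Day 180 row is a definite error in the shell. It should not be read as an extra visit or as lost data: Day 150 samples are scheduled, and Tables 35 and 37 report that visit.

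The denominator is at best unspecified. On the plain reading it is wrong for a by-visit percentage. The size is conditional: in a group of six with one member lacking the visit's result, 20% is shown as 17%; with no missing results there is no bias. This assumes that % is n over the header N, and that the missing participant entered the population through another visit's sample or an ET sample. Neither the number missing nor the number positive can be predicted from the documents.

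**What to change.** 1. In SAP section 11 and the Table 34 shell, define the % denominator as Immunogenicity Population participants with a valid screening-assay result at that time point. Show that count for each visit and treatment group beside the number positive. The header N can stay as the section 6.1 annotation.
2. Change the Day 180 row to Day 150.

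Table 36 needs no change on this account. The cost is a wording and shell edit to the SAP, with no new data or sampling. Where samples are missing, the percentages will rest on somewhat smaller denominators, which will be visible in the table.
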